8.3.5. Electrocardiograms

Single 12-lead ECGs will be obtained as outlined in the SoA (see [Table 3](#)) using an ECG machine that automatically calculates the heart rate and measures PR, QRS, QT, and QTc intervals. All 12-lead ECGs will be performed with the participant in a recumbent or semirecumbent position after 5 minutes of rest.

The 12-lead ECGs will be interpreted by the investigator at the site to be used for immediate participant management. Additional 12-lead ECGs may be performed as clinically indicated to manage participant safety. The decision to include or exclude a participant or discontinue study treatment based on an ECG flagged as "Abnormal, Clinically Significant" is the responsibility of the investigator, in consultation with the sponsor's medical monitor as appropriate. Clinically notable abnormalities that are considered clinically significant in the judgment of the investigator are to be reported as AEs. In the event that a single QTc is > 480 milliseconds at screening, the participant may enroll if the average QTc for the 3 ECGs is ≤ 480 milliseconds or with approval from the medical monitor. For participants with an intraventricular conduction delay (QRS interval > 120 milliseconds) at screening, the JTc interval may be used in place of the QTc with medical monitor approval. In addition, the JTc interval should be used for all subsequent assessments.

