5. STUDY POPULATION

Deviations from eligibility criteria are not allowed because they can potentially jeopardize the scientific integrity of the study, regulatory acceptability, and/or participant safety. Therefore, adherence to the criteria as specified in the Protocol is essential. Prospective approval of Protocol deviations to recruitment and enrollment criteria, also known as Protocol waivers or exemptions, are not permitted.

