| b | Hemoglobin | $\leq 9 \text{ g/dL}$ (transfusion allowed with a 2-week washout period) |
| c | ANC | $\leq 1.5 \times 10^9/\text{L}$ |
| Hepatic | | |
| d | ALT | $\geq 3 \times \text{ULN}$ ($> 5 \times \text{ULN}$ for liver metastasis) |
| e | AST | $\geq 3 \times \text{ULN}$ ($> 5 \times \text{ULN}$ for liver metastasis) |
| f | Total bilirubin | $\geq 1.5 \times \text{ULN}$ ($\geq 2.5 \times \text{ULN}$ if Gilbert's syndrome or liver metastasis) |
| g | Alkaline phosphatase | $\geq 3 \times \text{ULN}$ |
| Renal | | |
| h | Serum creatinine clearance | $\leq 30 \text{ mL/minute}$ based on Cockcroft-Gault formula |
| Chemistry | | |
| i | Serum phosphate | $> \text{ULN}$ |
| j | Serum calcium | Outside of normal range or serum albumin-corrected calcium outside of the normal range when serum albumin is outside of the normal range |

12. History of calcium and phosphate homeostasis disorder or systemic mineral imbalance with ectopic calcification of soft tissues (exception: commonly observed calcifications in soft tissues such as the skin, kidney tendon, or vessels due to injury, disease, or aging in the absence of systemic mineral imbalance).
13. Significant gastrointestinal disorder(s) that could interfere with absorption, metabolism, or excretion of study drug.
14. Clinically significant or uncontrolled cardiac disease including unstable angina, acute myocardial infarction within 6 months before Day 1 of study drug administration, New York Heart Association Class III or IV congestive heart failure, and uncontrolled arrhythmia (participants with pacemaker or with atrial fibrillation and well controlled heart rate are allowed).
15. History or presence of an abnormal ECG that, in the investigator's opinion, is clinically meaningful. A screening QTcF interval > 480 milliseconds is excluded. For participants with an intraventricular conduction delay (QRS interval > 120 ms), the JTc interval may be used in place of the QTc with medical monitor approval. The JTc must be ≤ 340 milliseconds if JTc is used in place of the QTc.
16. Active chronic or current infectious disease requiring systemic antibiotic, antifungal, or antiviral treatment within 2 weeks before enrollment (participants with asymptomatic chronic infections on prophylactic treatment are allowed).

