17. Evidence of active HBV or HCV infection (defined as participants with elevated transaminases or cirrhosis). Participants with chronic HBV/HCV infection with no cirrhosis and no elevated transaminases are allowed.
18. Participants with a known HIV infection who have CD4⁺ T-cell count < 350 cells/ μ L will be excluded. Participants with CD4⁺ T-cell (CD4⁺) counts \geq 350 cells/ μ L should generally be eligible.
19. Current use of prohibited medication as described in Section 6.6.2.
20. Use of any potent CYP3A4 inhibitors or inducers or moderate CYP3A4 inducers (see [Appendix D](#)) within 14 days or 5 half-lives (whichever is longer) before the first dose of study drug. Moderate CYP3A4 inhibitors are not prohibited but should be avoided (see Section 6.6.1).
21. Known hypersensitivity or severe reaction to pemigatinib or excipients of pemigatinib ([Pemazyre 2021a](#), [Pemazyre 2021b](#)).
22. Inability or unlikelihood of the participant to comply with the dose schedule and study evaluations, in the opinion of the investigator.
23. Inadequate recovery from toxicity and/or complications from a major surgery before starting therapy.
24. Women who are pregnant or breastfeeding. For Japan, women who are breastfeeding and wish to enroll must discontinue breastfeeding at least 90 days before receiving study drug. They must also refrain from breastfeeding during the course of study and for 90 days after the last dose of study drug.
25. Any condition that would, in the investigator's judgment, interfere with full participation in the study, including administration of study drug and attending required study visits; pose a significant risk to the participant; or interfere with interpretation of study data.
26. History of hypovitaminosis D requiring supraphysiologic doses (eg, 50,000 UI/weekly) to replenish the deficiency. Vitamin D supplements are allowed.
27. The following participants are excluded in France: vulnerable populations according to article L.1121-6 of the French Public Health Code and adults under legal protection or who are unable to express their consent per article L.1121-8 of the French Public Health Code.

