6.5.3. Criteria for Permanent Discontinuation of Study Drug

The occurrence of unacceptable toxicity not caused by the underlying disease will require that the study drug be permanently discontinued. Unacceptable toxicity is defined as follows:

- The occurrence of an AE that is related to study drug that, in the judgment of the investigator or the sponsor's medical monitor, compromises the participant's ability to continue study-specific procedures or is considered to not be in the participant's best interest.
- An AE requiring more than 2 dose reductions.
- A persistent AE requiring a delay of therapy for more than 2 weeks (14 days) unless a greater delay has been approved by the sponsor.
- An increase in QT/QTc to > 500 milliseconds or to > 60 milliseconds over baseline. In the case of a QTc > 500 milliseconds, the participant must be hospitalized, and continuous ECG monitoring must be set up until the measure of the QTc interval decreases below 500 milliseconds and is acceptable in the opinion of the local cardiologist. For elevations of the JTc interval, consultation with a cardiologist is recommended. A decision regarding dose modification or discontinuation of pemigatinib should be made in consultation with the sponsor's medical monitor.

See Section 7 for discontinuation procedures.

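### Section 8.3.5 lets a participant with a screening QTc above 480 ms enroll on medical monitor approval with no upper limit, while exclusion criterion 15 excludes that participant and Section 5 bars waivers

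*Protocol*

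**What the plan says.** **Exclusion criterion 15 (Protocol Section 5.2).** "A screening QTcF interval > 480 milliseconds is excluded". The criterion does not mention averaging. Its one exception applies when QRS exceeds 120 ms: JTc may then replace QTc if the medical monitor approves, and that route is capped: "The JTc must be ≤ 340 milliseconds if JTc is used in place of the QTc".

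**Waivers (Protocol Section 5).** "Prospective approval of Protocol deviations to recruitment and enrollment criteria, also known as Protocol waivers or exemptions, are not permitted".

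**ECG procedure (Protocol Section 8.3.5).** ECGs are taken singly. If one screening QTc exceeds 480 ms, the participant "may enroll if the average QTc for the 3 ECGs is ≤ 480 milliseconds or with approval from the medical monitor". The correction formula is not named, and no upper limit is attached to the approval.

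**Repeat tests (Protocol Sections 5.4 and 8.1.2).** A failing screening test may be repeated once if the investigator thinks the result was wrong. Section 8.1.2 adds that the latest result before treatment decides eligibility.

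**Stopping rule (Protocol Section 6.5.3, also Table 9).** Study drug is permanently discontinued for "An increase in QT/QTc to > 500 milliseconds or to > 60 milliseconds over baseline". A QTc above 500 ms also requires hospitalization and continuous ECG monitoring.

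**The concern.** In Section 8.3.5 the two routes are joined by *or*. Approval therefore matters only when the mean is not at or below 480 ms, which is the situation criterion 15 is meant to exclude. Where criterion 15 does give the monitor discretion, it states both the condition (QRS above 120 ms) and the ceiling (JTc 340 ms). The route in Section 8.3.5 has no stated ceiling and does not appear in criterion 15.

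Two things are at stake. The first is consistent eligibility: two sites following different sections could decide differently on the same participant. The second is safety: a participant admitted by approval starts closer to a limit that ends treatment and requires hospitalization.

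**Working it through.** There is no plan figure to reproduce. The check applies each rule to the same readings and then does simple arithmetic on the stopping rule.

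**Step 1. Apply the rules.** All readings are illustrative, in ms and in the order taken, with QRS ≤ 120 ms so that the JTc exception does not apply.

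| Case | Readings | Mean | Criterion 15 | Latest result (8.1.2) | Section 8.3.5 |
|---|---|---|---|---|---|
| 1 | 495, 490, 485 | 1470/3 = 490 | Excluded whichever reading is used | 485: excluded | Enrollable with approval |
| 2 | 505, 490, 475 | 1470/3 = 490 | Depends on which reading counts | 475: passes | Fails on the mean; enrollable with approval |
| 3 | First 490, three-ECG mean 475 | 475 | First reading excluded; no averaging rule | Depends on last reading | Enrollable on the mean, no approval needed |
| 4 | Three-ECG mean 510 | 510 | Excluded if the reading used is above 480 | Depends on last reading | Enrollable with approval, since no ceiling is stated |

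Case 1 is the direct conflict, because no choice of reading removes it. Cases 2 and 3 show the second problem, that the protocol does not settle which value counts. Three readings already go beyond the single repeat in Sections 5.4 and 8.1.2, so the repeat rules and Section 8.3.5 were not written to fit together. Case 4 follows from the literal wording: the mean is already above the 500 ms level in the stopping rule.

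**Step 2. Distance to the stopping limit.** Let b be the baseline QTc, assumed equal to the screening value. From Section 6.5.3, the largest rise that does not trigger discontinuation is min(500 − b, 60).

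| b (ms) | 500 − b | Largest rise without stopping (ms) | Smallest whole-ms rise that stops treatment |
|---|---|---|---|
| 440 | 60 | 60 | 61 |
| 480 | 20 | 20 | 21 |
| 490 | 10 | 10 | 11 |
| 499 | 1 | 1 | 2 |

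The two limbs of the rule meet where 500 − b = 60, that is, at b = 440 ms. Above that, the 500 ms limb is reached first.

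**Step 3. Time to the next scheduled ECG.** In the 12-lead ECG row of Table 3, the next on-treatment ECG after Cycle 1 Day 1 is Cycle 3 Day 1. With 21-day cycles this is Day 2 × 21 + 1 = 43 (± 3 days), or 42 days after Day 1, unless an ECG is clinically indicated or treatment ends earlier.

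**The case against.** **Section 5 already governs.** It is the eligibility section, it treats adherence as essential, and it bars waivers; Section 8.3.5 is an assessment procedure. On that reading criterion 15 prevails and only tidying is needed. This has force as interpretation. However, Section 8.3.5 states in terms that the participant may enroll, and the sponsor could equally call it a written exception and not a waiver. Neither section refers to the other on this point, so the conflict remains.

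**A mean above 480 ms always breaches Section 5.2.** A reader might infer this, but the documents do not support it. Criterion 15 does not use a mean, and Section 8.1.2 takes the latest repeat, so case 2 could pass. The conflict is certain only where all readings, or at least the one that counts, exceed 480 ms.

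**The wording exposes participants to unguarded QT risk.** A reader might infer this too, and it goes too far. The monitor may refuse approval. The investigator-judgment exclusions still apply: criterion 14 ("Clinically significant or uncontrolled cardiac disease"), the opening of criterion 15 ("History or presence of an abnormal ECG") where the investigator finds it clinically meaningful, and criterion 25 for conditions that "pose a significant risk to the participant". An ECG is scheduled on Day 1, and the stopping rules apply. The 42-day gap is the same for every participant and is not caused by this wording. Section 2.3 does not name QT prolongation among the drug's risks. What stands is that none of the judgment-based exclusions sets a numeric limit.

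**Monitor discretion is a legitimate choice.** That is fair. It could be kept, but it would need to appear in criterion 15 with a ceiling.

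**The terminology points are minor.** Agreed. Criterion 15 itself moves between QTcF and QTc, and Section 8.3.5 allows additional ECGs when clinically indicated, so its mention of three is under-described and not contradictory.

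**Conclusion.** The point holds. For a participant with QRS of 120 ms or less and every screening reading above 480 ms, Section 5.2 excludes and Section 8.3.5 permits enrollment on an approval with no ceiling. Separately, three rules disagree on whether a single reading, the mean or the latest reading decides.

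The practical size is modest. At 490 ms the margin to mandatory discontinuation is 10 ms, against 20 ms at the 480 ms cap. These margins assume that baseline equals the screening value. The cap applies at screening, so it guarantees no margin at first dose. The documents give no count of participants affected; it is probably small. The effect is on consistent eligibility and participant safety. Nothing here changes the sample size or the primary ORR analysis. It is worth correcting at the next amendment.

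**What to change.** 1. **Section 8.3.5.** In the sentence on a single screening QTc above 480 ms, delete the medical monitor approval alternative and write QTcF for QTc.
2. **Criterion 15.** Add: *If a single screening QTcF is > 480 ms, 2 further screening ECGs are taken; notwithstanding the repeat-test rules in Sections 5.4 and 8.1.2, the mean QTcF of the 3 ECGs decides eligibility and must be ≤ 480 ms.*

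The override clause is needed because those sections allow one repeat, and Section 8.1.2 uses the latest value. Without it the new sentence would create a fresh conflict. The JTc rule and the waiver ban stay as they are.

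With these edits cases 1, 2 and 4 are excluded and case 3 enrolls, whichever section a site consults. Averaging still protects against one spurious reading.

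**Cost.** Two wording edits at the next amendment and no new assessment, since Section 8.3.5 already relies on three ECGs. The medical monitor loses discretion over borderline participants, and someone in case 2 can no longer enter on a low last reading. If the sponsor prefers to keep the discretion, criterion 15 should state the approval route with a numeric ceiling; the documents give no value for one.

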8.3.6. Comprehensive Eye Examination

A comprehensive eye examination should be performed by a qualified ophthalmologist at screening, once every 3 cycles (\pm 7 days, starting at Cycle 3), at EOT, and as clinically indicated. The eye examination should include a visual acuity test, slit-lamp examination, fundoscopy with digital imaging, and OCT. Every effort should be made to ensure that all subsequent examinations are performed by the same ophthalmologist.

Per CTCAE v5.0, retinal detachment is graded as 3 (macular sparing) and 4 (macula-off), but this refers to rhegmatogenous retinal detachment (when a hole occurs in the retina). There is no grading for SRD/RPED (no hole in the macula, just fluid accumulation). Therefore, grading should be based on the CTCAE v5.0 term of retinopathy.

8.3.7. Laboratory Assessments

See [Table 12](#) for the list of clinical laboratory tests to be performed and [Table 4](#) for the timing and frequency. A certified laboratory local to the investigative site will perform all clinical laboratory assessments for safety (ie, blood chemistries, hematology assessments, coagulation tests, endocrine function, and urinalysis). The investigative site will enter the laboratory results and laboratory normal ranges into the eCRF. Additional testing may be required by the sponsor based on emerging safety data. Additional tests may also be performed if clinically indicated.

A central laboratory will analyze all PK and translational samples. Information regarding collection, processing, and shipping of laboratory assessments is provided in the Laboratory Manual.

Serum phosphate testing is required on Day 8 in Cycles 2+ if a participant develops HP during Cycle 1. Parathyroid hormone (endocrine) testing is required at baseline and Day 1 of every third cycle (starting with Cycle 3) as parathyroid hormone plays a role in calcium and phosphate hemostasis ([Khundmiri et al 2016](#)).

Clinically significant abnormal laboratory findings are those that are not associated with the underlying disease, unless judged by the investigator to be more severe than expected for the participant's condition. All laboratory tests with values considered clinically significantly abnormal during participation in the study or within 30 days after the last dose of study treatment should be repeated until the values return to normal or baseline or are no longer considered clinically significant by the investigator or medical monitor.

Screening laboratory assessments for hematology, chemistry, and coagulation must be performed within 14 days before Cycle 1 Day 1. If performed more than 14 days before Cycle 1 Day 1, then the tests must be repeated and eligibility confirmed before study treatment administration on Cycle 1 Day 1.

Laboratory sample collection on Cycle 1 Day 1 must be performed before study treatment administration. After Cycle 1, predose laboratory procedures can be conducted up to 72 hours before study treatment administration (within the 3-day study window), and results should be reviewed by the investigator or qualified designee and found to be acceptable before a new cycle of treatment is initiated.

Table 12: Required Laboratory Analytes

| Blood Chemistries | Hematology | Urinalysis With Microscopic Examination | Serology | Coagulation |
|--|---|---|--|-------------|
| Albumin | Complete blood count, including: | Color and appearance | HBsAg | PT |
| Alkaline phosphatase | 
 • Hemoglobin • Hematocrit • Platelet count • Red blood cell count • WBC count | pH and specific gravity | HBsAg antibody | PTT or aPTT |
| ALT | | Bilirubin | Hepatitis B core antibody | INR |
| AST | | Glucose | HCV antibody | |
| Amylase | | Ketones | NOTE: If any of the above are positive, HBV-DNA, HCV-RNA may be done to assess risk of reactivation, if indicated (eg, no history of immunization) | |
| Bicarbonate or CO ₂ (not applicable in Japan) | | Leukocytes | | |
| Blood urea nitrogen or urea | | Nitrite | | |
| Calcium | | Occult blood | | |
| Chloride | | Protein | | |
| Creatinine | | | | |
| Glucose | | | | |
| Lactate dehydrogenase | | | | |
| Lipase | | | | |
| Magnesium | | | | |
| Phosphate | | | | |
| Potassium | | | | |
| Sodium | | | | |
| Total bilirubin | | | | |
| Direct bilirubin (if total bilirubin is elevated above ULN) | Absolute values must be provided for: | | | |
| Total protein | 
 • WBC differential laboratory results | | | |
| Uric acid | | | | |
| Vitamin D (25-hydroxyvitamin D and 1,25-dihydroxyvitamin D) ^a | | | | |

Note: Additional tests may be required, as agreed upon by the investigator and sponsor, based on emerging safety data or to rule out a diagnosis.

^a Results not required prior to dose administration.

8.3.7.1. Pregnancy Testing

A serum pregnancy test will be required for all WOCBP during screening and at the EOT and safety follow-up visits; participants going into hospice are not required to have an EOT pregnancy test. Urine pregnancy tests will be performed locally on Day 1 of each cycle, as outlined in [Table 4](#), as medically indicated (eg, in case of loss of menstrual cycle, when pregnancy is suspected), or per country-specific requirement (note that country-required urine pregnancy testing will be outlined and communicated to investigational sites under separate cover). If a urine pregnancy test is positive, the results should be confirmed with a serum pregnancy test.

If the serum pregnancy test is negative after a urine test was positive, the investigator will assess the potential benefit/risk to the participant and determine whether it is in the participant's best interest to resume study drug and continue participation in the study.

If a pregnancy is confirmed by a serum pregnancy test, see Section [9.7](#) for reporting requirements.

8.3.7.2. Serology

Serology assessments will be performed at the screening visit to rule out hepatitis infection; required analytes are shown in [Table 12](#). Generally, hepatitis tests should be performed early in the screening process due to the length of time needed to obtain the results. Additional tests may be performed if clinically indicated.

8.4. Pharmacokinetic Assessments

Plasma samples will be collected for the measurement of plasma concentrations of pemigatinib as specified in [Table 4](#) and [Table 13](#). A maximum of 8 samples may be collected at additional timepoints during the study if warranted and agreed upon between the investigator and the sponsor. Samples collected for analyses of pemigatinib plasma concentrations may also be used to evaluate safety or efficacy aspects related to concerns arising during or after the study. The actual date and time (24-hour clock time) of each sample will be recorded. Instructions for the collection and handling of biological samples will be provided in the Laboratory Manual.

8.4.1. Blood Sample Collection

Pharmacokinetic samples will be obtained at the visits indicated in [Table 4](#). The exact date and time of the PK blood draws will be recorded in the eCRF along with the date and time of the last dose of study drug preceding the blood draw and the time of the most recent meal. Instructions for sample preparation and shipping will be provided in the Laboratory Manual. Participants will receive reminder cards prior to the study visit providing instruction to hold the dose of study drug on the day of the visit. During Cycle 1, PK samples will be obtained on Day 8. The participant must refrain from eating 8 hours before arriving at the site. A trough (predose) PK sample will be drawn early in the study visit; the sample must be drawn approximately 1 hour before study drug administration. A 5-minute window can be applied to PK sample collection at 1 and 2 hours postdose. Participants then need to fast for 1 additional hour after taking study medication. Once the participant takes the study drug, any subsequent timed samples will be taken as per [Table 13](#).

Table 13: Pharmacokinetic Blood Sample Timing

| Study Visit | Timing of Sample |
|---------------|--|
| Cycle 1 Day 8 | 
• Predose• 1 hour postdose• 2 hours postdose• 4-12 hours postdose |

